10.3. Data Protection and Confidentiality

Study patients must be informed that his/her personal study-related data will be used by the sponsor in accordance with local data protection law. The level of disclosure must also be explained to the patient who will be required to give consent for their data to be used as described in the informed consent.

Patients must be informed that his/her medical records may be examined by Clinical Quality Assurance auditors or other authorized personnel appointed by the sponsor, by appropriate IRB/IEC members, and by inspectors from regulatory authorities.

Participants will be assigned a unique identifier by the sponsor. Any participant records, datasets or tissue samples that are transferred to the sponsor will contain the identifier only; participant names or any information which would make the participant identifiable will not be transferred.

The Sponsor has processes in place to ensure data protection, information security and data integrity. These processes include appropriate contingency plan(s) for appropriate and timely response in the event of a data security breach.

10.4. Study Documentation and the eCRF

This protocol is to be signed by the investigator responsible for the conduct of this study at the study site. A copy of the signed protocol signature page is to be provided to the Sponsor and retained in the study site's Regulatory Binder.

The Investigator is responsible for ensuring that all study data are accurately recorded on the eCRFs or other study data collection tools. All eCRF entries must be supported by the patient's medical records or source notes. The Investigator must ensure that study observations and findings are legible and recorded accurately and completely.

Original reports, traces and films must be reviewed, signed and dated, and retained by the Investigator for future reference.

The Investigator is expected to promptly review all study data recorded in the patient's source records. Completed eCRFs must be promptly reviewed, signed, and dated by the Investigator or Sub-Investigator at the end of the study. Corrections to data entered into the eCRF will be handled through an electronic query. Corrections to patients' medical or source records should be legible, initialed and dated. At the end of the study, an electronic copy of the investigator's eCRFs will be provided to the Investigator. The Investigator is to retain these data. The Investigator will maintain a signature sheet to document signatures and initials of all persons authorized to make entries and/or corrections on eCRFs. Refer to Section 10.6 regarding retention requirements.

An Investigator is required to prepare and maintain adequate and accurate case histories designed to record all observations and other data pertinent to the investigation for each patient treated with the study drug or entered as a control in the investigation. Data reported on the eCRFs that are derived from source documents must be consistent with the source documents or the discrepancies must be explained.

10.5. Study Monitoring

The Sponsor or designee will be responsible for the monitoring of the study. Study monitors will contact and visit the Investigators at regular intervals throughout the study to verify adherence to the protocol, and assess the completeness, consistency, and accuracy of the data by comparing patients' medical records with entries in the eCRF.

The study monitor must be allowed access to laboratory test reports and other patient records needed to verify the entries on the eCRF, provided patient confidentiality is maintained in accordance with local requirements. These records, and other relevant data, may also be reviewed by appropriate qualified personnel independent from the Sponsor or designee, who is appointed to audit the study. Patient confidentiality will be maintained at all times.

By agreeing to participate in this research study, the Investigators agree to co-operate with the study monitor to ensure that any problems detected during the monitoring visits are promptly resolved.

10.6. Retention of Study Documentation

The Investigator must retain study drug disposition records, copies of CRFs and all study-related source documents for the maximum period required by applicable regulations and guidelines, or

Institution procedures, or for the period specified by the Sponsor, whichever is longer. The Investigator must contact the Sponsor prior to destroying any records associated with the study.

If the Investigator withdraws from the study (e.g., relocation, retirement), the records shall be transferred to a mutually agreed upon designee (e.g., another Investigator, IRB). Notice of such transfer will be given in writing to the Sponsor or designee.

If the Investigator cannot guarantee this archiving requirement for any or all the documents at the investigational site, arrangements must be made between the Investigator and the Sponsor to store these in a secure archive facility outside the site so they can be returned to the Investigator in case of a regulatory audit. When source documents are required for the continued care of the patient, appropriate copies should be made for storage outside of the site.

10.7. Data Publication

In accordance with the sponsor's publication policy the results of this study will be submitted for publication by a peer-reviewed journal.

12. APPENDICES

APPENDIX 1. SCHEDULE OF VISITS AND PROCEDURES

Study Procedure	Screening	Baseline	Treatment														Safety	
	Day (D): Week (W)	D1	W2 ±3d	W4 ±3d	W6 ±3d	W8 ±3d	W12 ±3d	W16 ±3d	W20 ±5d	W24 ±5d	W28 ±5d	W32 ±5d	W36 ±5d	W40 ±5d	W44 ±5d	W48 ±5d	W52/ET ±5d	12W Post ±5d
Visit Window	1	2	3	4	5	6	7	8	9	10	11	12	13	14	15	16	17	18
Visit Number	1	2	3	4	5	6	7	8	9	10	11	12	13	14	15	16	17	18
Informed Consent/Assent	X																	
Inclusion/Exclusion, Med Hx, Demographics	X	X																
Review Immunization Record	X																	
Safety																		
Vital Signs	X	X	X	X	X	X	X	X	X	X	X	X	X	X	X	X	X	X
Physical Exam, Weight/Height	X							X				X					X	
HIV, Hepatitis	X																	
Hematology, Chemistry, Urinalysis	X					X		X				X					X	
Pregnancy Test	Serum	urine		urine		urine	urine	urine	urine	urine	urine	urine	urine	urine	urine	urine	urine	
Hormone Testing ¹	X							X				X					X	
Adverse Events			X	X	X	X	X	X	X	X	X	X	X	X	X	X	X	X
Concomitant Meds & Procedures	X	X	X	X	X	X	X	X	X	X	X	X	X	X	X	X	X	X
Efficacy and Patient Reported Outcomes																		
IGA, BSA, EASI	X	X		X		X		X				X					X	
DLQI/CDLQI ²		X						X				X					X	
PROMIS Anxiety & Depression ²		X						X				X					X	
Pharmacokinetics (PK) and Immunogenicity (ADA)																		
Pre-dose PK		X		X				X				X					X	X
Pre-dose ADA ³		X		X				X				X					X	X
Study Drug																		
Administer Study Drug		X	X	X	X	X	X	X	X	X	X	X	X	X	X	X	X	
Instruction on Self-Administration						X												
Dispense Drug for At-Home Injection						X	X	X	X	X	X	X	X	X	X	X		

¹ Collect estradiol for females only. Collect testosterone for males only ² Patient reported outcome and quality of life measures should all be completed prior to other study assessments; ³ nAB testing conducted for positive treatment-emergent ADA responses. Additional immunogenicity sample collected for any patient experiencing a hypersensitivity reaction during study.

APPENDIX 2. AMERICAN ACADEMY OF DERMATOLOGY CONSENSUS CRITERIA FOR CHRONIC ATOPIC DERMATITIS

Atopic dermatitis: Diagnosis recommendations

Patients with presumed atopic dermatitis should have their diagnosis based on the criteria summarized below. On occasion, skin biopsy specimens or other tests (such as serum immunoglobulin E, potassium hydroxide preparation, patch testing, and/or genetic testing) may be helpful to rule out other or associated skin conditions.

Level of Evidence: III Strength of Recommendation: C

Essential features — must be present:

- Pruritus
- Eczema (acute, subacute, chronic)
- Typical morphology and age specific patterns*
- Chronic or relapsing history

*Patterns include:

1. Facial, neck, and extensor involvement in infants and children
2. Current or previous flexural lesions in any age group
3. Sparing of the groin and axillary regions

Important features — seen in most cases, adding support to the diagnosis:

- Early age of onset
- Atopy
- Personal and/or family history
- Immunoglobulin E reactivity
- Xerosis

Associated features — These clinical associations help to suggest the diagnosis of atopic dermatitis but are too nonspecific to be used for defining or detecting atopic dermatitis for research and epidemiologic studies:

- Atypical vascular responses (e.g., facial pallor, white dermographism, delayed blanch response)
- Keratosis pilaris/ pityriasis alba/ hyperlinear palms/ ichthyosis
- Ocular/periorbital changes
- Perifollicular accentuation/ lichenification/ prurigo lesions

Exclusionary conditions — It should be noted that a diagnosis of atopic dermatitis depends on excluding conditions, such as:

- Scabies
- Seborrheic dermatitis
- Contact dermatitis (irritant or allergic)
- Ichthyoses
- Cutaneous T-cell lymphoma
- Psoriasis
- Photosensitivity dermatoses
- Immune deficiency diseases
- Erythroderma of other causes

adapted from [Eichenfield, 2014](#).

DLQI	Dermatology Life Quality Index
DMC	Data Monitoring Committee
DSMB	Data Safety Monitoring Board
DSUR	Development Safety Update Report
EASI	Eczema Area and Severity Index
EASI-50	Eczema Area and Severity Index improvement of $\geq 50\%$
EASI-75	Eczema Area and Severity Index improvement of $\geq 75\%$
EASI-90	Eczema Area and Severity Index improvement of $\geq 90\%$
eCRF	electronic case report form

HLT	high-level term
ICH	International Conference on Harmonisation
IGA	Investigator's Global Assessment
ISR	injection site reactions
Lilly	Eli Lilly and Company
LOCF	last observation carried forward
MCMC	Markov chain Monte Carlo
MedDRA	Medical Dictionary for Regulatory Activities
MI	multiple imputation
NAb	Neutralizing anti-drug antibodies
NMSC	non-melanoma skin cancer
OI	opportunistic infection
PD	pharmacodynamic
PhUSE	Pharmaceutical Users Software Exchange
PK	pharmacokinetic
PROMIS	Patient-Reported Outcomes Information System
PT	Preferred Term
Q2W	every 2 weeks
SAE	serious adverse event
SAP	statistical analysis plan
SE	standard error
SMQ	Standardized MedDRA Query
SOC	System Organ Class
TBL	total bilirubin
TE-ADA	treatment-emergent ADA
TEAE	treatment-emergent adverse event
WHO	World Health Organization

4. Revision History

Statistical Analysis Plan Version 1 was approved prior to database lock on September 14, 2020.

Statistical Analysis Plan Version 2 was approved prior to database lock on January 18, 2022.

Statistical Analysis Plan Version 3 was approved prior to database lock.

Changes in Version 2 and Version 3 are documented in the following 2 tables. Minor corrections/additions may not be included.

Revisions in SAP Version 2:

Section	Action
Section 7.3.3	Added Section 7.3.3. Markov chain Monte Carlo - Multiple Imputation (MCMC-MI)
Section 7.13.2	Removed sentence related to AE starting time, since the AE starting time was not collected
Section 7.10	Updated the BSA total calculation in Table KGAE.7.3
Section 7.13.6.3	Added new analyses in Table KGAE.7.10
Section 7.13.6.4	Added new analysis in Table KGAE.7.11
Section 7.13.6.5	Added new analyses in Table KGAE.7.12
Section 7.13.6.8	Added Section 7.13.6.8. Atopic Dermatitis Exacerbation
Section 7.13.6.9	Added Section 7.13.6.9. Suicide/Self-Injury
Throughout the document	Minor editorial changes and/or clarifications were made

Abbreviations: AE = adverse event; BSA = body surface area.

Revisions in SAP Version 3:

Section	Description of Change	Rationale
Section 7.1.1	Added “enrolled” to the definition of the safety population in the body text and in Table KGAE.7.1	Clarification
Section 7.3.1	Added health outcome endpoints to the “as-observed” analyses	Clarification
Section 7.3.2	Updated LOCF strategy	Clarification on strategy for values collected subsequent to treatment discontinuation.
Section 7.3.3	
 Updated MCMC-MI strategy Removed PROMIS measures from Table KGAE.7.2, and updated DLQI/CDLQI analyses 	
 Clarification on strategy for imputing baseline. Address strategy for values collected subsequent to treatment discontinuation. Correction to details of SAS code implementation. Correction
Section 7.7.1	Updated subcategories for AD treatments used in the past	Clarification
Section 7.9	Updated description of rescue medications	Clarification

Section	Description of Change	Rationale
Section 7.10	
 1. Added detail for construction of confidence intervals 2. Updated DLQI(0,1), CDLQI(0,1), and DLQI 4-point improvement variable definitions in Table KGAE.7.3 3. Removed CDLQI 4-point improvement endpoint from Table KGAE.7.3 	
 1. Clarification 2. Clarification 3. There is no established minimum clinically important difference for CDLQI
Section 7.11	Added detail for construction of confidence intervals	Clarification
Section 7.13.1	Added sentence about systemic therapy use with respect to exposure calculation	Clarification
Appendix 1	Added definition of rescue medications	To provide detailed instructions on how to determine rescue medications for this study

Abbreviations: AD = atopic dermatitis; CDLQI = Children’s Dermatology Life Quality Index; DLQI = Dermatology Life Quality Index; LOCF = last observation carried forward; MCMC-MI = Markov chain Monte Carlo-multiple imputation.

5. Study Objectives

Table KGAE.5.1 shows the protocol-defined objectives and endpoints of the study. In addition, the summaries of some non-protocol-defined endpoints are described in Section 7.10 to provide supportive evidence of efficacy.

Table KGAE.5.1. Protocol-Defined Objectives and Endpoints

Study Objective: To evaluate the safety and efficacy of lebrikizumab in adolescent patients (≥ 12 to < 18 years weighing ≥ 40 kg) with moderate-to-severe AD.


Primary Endpoint: Describe the proportion of patients discontinued from study treatment due to adverse events through the last treatment visit.

Secondary Endpoints: Over the duration of the study:
 
 • Percentage of patients with an IGA score of 0 or 1 and a reduction ≥ 2-points from baseline • Percentage of patients achieving response of Eczema Area and Severity Index improvement of $\geq 75\%$ (EASI-75) ($\geq 75\%$ reduction from baseline in EASI score) • Percentage change from baseline in EASI score and percentage of patients achieving Eczema Area and Severity Index improvement of $\geq 50\%$ (EASI-50) and Eczema Area and Severity Index improvement of $\geq 90\%$ (EASI-90) (≥ 50 and $\geq 90\%$ reduction from baseline in EASI score, respectively) • Change from baseline in body surface area (BSA) • Change from baseline in Patient-Reported Outcomes Information System (PROMIS)[®] Anxiety and Depression measures • Change from baseline and improvement in Dermatology Life Quality Index (DLQI)/Children's Dermatology Life Quality Index (CDLQI) • Pharmacokinetics (PK)

Abbreviations: IGA = Investigator's Global Assessment; AD = atopic dermatitis.

6. Study Design

6.1. Summary of Study Design

Study J2T-DM-KGAE (KGAE) (also known as DRM06-AD17) is an open-label, single-arm study to assess the safety and efficacy of lebrikizumab in adolescent patients with moderate-to-severe AD. A sample size of approximately 200 adolescent patients (≥ 12 to < 18 years, weighing ≥ 40 kg) is planned.

The study is composed of a 52-week treatment period, with the last study drug injection at Week 50. Patients completing this 52-week study will be offered active lebrikizumab treatment in a separate long-term extension study, J2T-DM-KGAA (DRM06-AD07). Patients who early terminate or choose not to enter the long-term extension study will undergo a safety follow-up visit approximately 12 weeks after the last study drug injection.

6.1.1. Screening

Screening Period: Patients will be evaluated for study eligibility before the baseline visit (Day 1).

6.1.2. Baseline and Week 2

Patients who meet eligibility criteria are assigned to receive 250-mg lebrikizumab Q2W. At the baseline and Week 2 clinic visits, all patients will be administered a loading dose of 500-mg lebrikizumab as two 2-mL, 250-mg (125-mg/mL) prefilled syringes with a preassembled needle safety device.

6.1.3. Week 4 to Week 52

Patients will return to the clinic at Weeks 4, 6, 8, and every 4 weeks thereafter through Week 52 for safety and efficacy assessments. For Weeks 4 through 50, all patients will be administered one 250 mg lebrikizumab syringe, Q2W. Study drug injections will be administered in the clinic through Week 8 and patients or their caregivers will be instructed on self-administration of the study drug for injections following the Week 8 visit. The clinic visit at Week 52 is the end of the treatment period. Patients completing this 52-week study will be offered active lebrikizumab treatment in a separate long-term extension study (DRM06-AD07/J2T-DM-KGAA).

6.1.4. Safety Follow-up Visit

Patients who early terminate or choose not to enter the long-term extension study will undergo a safety follow-up visit approximately 12 weeks after the last study drug injection.

6.2. Determination of Sample Size

The logo for CCI (Clinical Care Innovations) is displayed in red text on a black background.

6.3. Method of Assignment to Treatment

This is a single-arm study. All enrolled patients are assigned to 250-mg lebrikizumab Q2W.

7. A Priori Statistical Methods

7.1. General Considerations

Statistical analysis of this study will be the responsibility of Lilly. The latest version of the MedDRA will be used.

Summaries from assessment of endpoints described in the protocol are planned to be included in a CSR. Summaries for key safety data are also planned to be included in the CSR. Results from additional efficacy summaries and other safety summaries may also be provided in the CSR as deemed appropriate.

Any change to the data analysis methods described in the protocol will require a protocol amendment ONLY if it changes a principal feature of the protocol. Any other change to the data analysis methods described in the protocol and the justification for making the change will be described in the CSR.

All statistical processing will be performed using SAS® unless otherwise stated.

The schedule of visits and procedures outlined in the protocol specifies the allowable windows for assessments. Assessments performed outside these windows will not be excluded from any summaries, unless specified otherwise.

7.1.1. Analysis Populations

All non-PK analyses will be performed using the safety population. All enrolled patients who receive at least 1 confirmed dose of lebrikizumab 250 mg will be included in the safety population.

All PK analyses will be performed using the PK population. All patients who are enrolled and have a predose sample and at least 1 postdose analyzable sample will be included in the PK population.

All entered patients, consisting of all patients who signed informed consent, and the safety population, will be used to summarize patient disposition. These populations will also be used for listings.

The number of patients included in each population will be summarized.

[Table KGAE.7.1](#) describes the analysis populations.

Table KGAE.7.1. Analysis Populations

Population	Description
All Entered Patients	All patients who signed informed consent. Patient flow will be summarized.
Safety Population	All enrolled patients who received at least 1 confirmed dose of lebrikizumab 250 mg. All non-PK analyses will be performed using the safety population.
PK Population	All patients who are enrolled and have a predose sample and at least 1 postdose analyzable sample. All PK analyses will be performed using this population.

Abbreviations: PK = pharmacokinetic(s).

7.1.2. General Considerations for Analyses

Data will be summarized using descriptive statistics. No inferential testing will be performed. Categorical variables will be tabulated with frequencies and percentages. Continuous variables will be tabulated with mean, median, standard deviation, and range (minimum and maximum).

Baseline will be defined as the last available value before the first injection for efficacy and health outcome analyses. In most cases, this will be the measure recorded at the baseline visit (Day 1). If the patient does not take any injection, the last available value on or prior to treatment assignment date will be used. Change from baseline will be calculated as the visit value of interest minus the baseline value.

For the safety analyses, the following baselines will be used. For safety analyses using a baseline period, the baseline period is defined as the time from the screening visit to the date/time of the first injection

- TEAEs: baseline will be all results recorded during the baseline period.
- Treatment-emergent abnormal laboratory and vital signs results: baseline will be all results recorded during the baseline period.
- Change from baseline to last postbaseline observation or to each scheduled postbaseline visit for laboratory and vital signs results: baseline will be the last scheduled nonmissing assessment recorded during the baseline period.

7.2. Adjustments for Covariates

No statistical tests will be performed.

7.3. Handling of Dropouts or Missing Data

Intercurrent events, as per the ICH guideline (ICH E9R1), are events which occur after the treatment initiation and make it impossible to measure a variable or influence how it should be interpreted. Examples of such events include treatment discontinuation due to death or AEs, rescue treatment, and loss to follow-up.

This section describes missing data imputation methods handling intercurrent events, which will be implemented in this study.

7.3.1. As Observed Analysis

The “as observed” strategy is used in so-called “observed cases” or “completers” analysis ubiquitous in the literature but is not one of the recommended strategies in the ICH E9(R1). For this analysis, only data from completers at the visit are relevant. Therefore, this estimand is conditional and targets the effect of treatment conditional on completion of treatment through the time point of interest. Because the estimand is defined for a subpopulation conditional on an intercurrent event, it is not causal. Summaries based on observed data at each postbaseline visit will be provided. All efficacy and health outcome endpoints will be summarized using an “as observed” analysis.

A large, stylized red watermark consisting of the letters 'CCI' is centered on a solid black rectangular background. The letters are bold and serifed.

The image shows the letters 'CCI' in a large, bold, red serif font. The letters are set against a solid black rectangular background that occupies the upper half of the page.

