6.3. Treatments for AD

TCS, TCIs and PDE4 inhibitors may be used as needed to treat disease flares during the trial. Patients who may require short-term systemic treatment for symptoms of AD will be assessed on a case-by-case basis and must be discussed with the Medical Monitor prior to initiating treatment.

Cannabinoid treatments for AD are prohibited.

Patients requiring long-term systemic treatment for symptoms of AD (e.g., non-responders) must be discontinued from the study.

Medications used for AD must be recorded in the eCRF.

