8.6.1. Early Termination of Study Patients

The Investigator will make reasonable efforts to keep each patient in the study. However, patients may terminate or be terminated early from the study for the following reasons:

- Voluntarily withdrawal of consent to participate in the study participation, at any time
- Adverse event, laboratory abnormality or inter-current illness which, in the opinion of the Investigator, indicates that continued treatment and/or participation in the study is not in the best interest of the patient
- Serious protocol violation, persistent non-compliance or requirement for medication or procedure prohibited by the protocol
- Lost to follow-up

Patients who are terminated early from the study will have an Early Termination visit scheduled as soon as possible (see Section 7.18). All information, including the reason for early termination will be recorded in the patient's study records and in the eCRF.

Two attempts of contact (e.g., telephone contact) followed by a certified letter of contact to the patient must be documented in a patient's study records for all patients who are believed to be lost to follow-up.

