8.6.2. Study Drug Discontinuation

Study drug must be discontinued for patients who experience the following:

- Inter-current illness that would, in the judgment of the Investigator, affect assessments of clinical status to a significant degree
- Treatment-related AEs that are clinically significant, deemed persistent, in the judgment of the Investigator
- Unacceptable toxicity
- Pregnancy
- Use of rescue medication as outlined in Section 6.3

Patients who discontinue study drug permanently during study participation must be scheduled for an Early Termination visit (Section 7.18).

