7.10. Efficacy Analyses

[Table KGAE.7.3](#) includes the description and derivation of the efficacy measures and endpoints.

For categorical parameters, the number and percentage of patients in each category will be presented, as well as a 95% confidence interval for the percentage. The 95% confidence interval

will be constructed using the asymptotic method, without continuity correction (that is, the normal approximation to the binomial distribution). For continuous parameters, descriptive statistics will include n (number of patients), mean, standard deviation, median, minimum, and maximum. These summaries will be provided for the data as-observed, and after implementation of LOCF and MCMC-MI imputation methods.

The IGA, EASI, and BSA will be reported by clinic visit.

Table KGAE.7.3. Description and Derivation of Efficacy/Health Outcomes Measures and Endpoints

Measure	Description	Variable	Derivation/Comment	Imputation Approach if Missing Components
Investigator’s Global Assessment (IGA)	The IGA is a static assessment and rates the severity of a patient’s AD. The IGA is comprised of a 5-point scale ranging from 0 (clear) to 4 (severe), and a score is selected using descriptors that best describe the overall appearance of the lesions at a given time point.	IGA score	Single item. Range: 0-4 0 represents “clear” 4 represents “severe”	Single item, missing if missing
		
 IGA (0,1) with ≥2-point improvement^a IGA (0) 	
 Observed score of 0 or 1 and change from baseline ≤-2 Observed score of 0 	Missing if baseline or observed value is missing Single item, missing if missing

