Eczema Area and Severity Index (EASI)	The EASI scoring system uses a defined process (Steps 1-5 below) to grade the severity of the signs of eczema and the extent affected. The extent of disease (percentage of skin affected: 0 = 0%; 1 = 1-9%; 2 = 10-29%; 3 = 30-49%; 4 = 50-69%; 5 = 70-89%; 6 = 90-100%) and the severity of 4 clinical signs (erythema, edema/papulation, excoriation, and lichenification) each on a scale of 0-3 (0 = none, absent; 1 = mild; 2 = moderate; 3 = severe) at 4 body sites (head and neck, trunk, upper limbs, and lower limbs). Half scores are allowed between severities 1, 2, and 3. Each body site will have a score that ranges from 0-72, and the final EASI score will be obtained by weight-averaging these 4 scores. Hence, the final EASI score will range from 0-72 for each time point.	EASI score	Derive EASI region score for each of head and neck, trunk, upper limbs, and lower limbs as follows: $EASI_{region} = (\text{erythema} + \text{edema/papulation} + \text{excoriation} + \text{lichenification}) * (\text{value from percentage involvement})$, where erythema, edema/papulation, excoriation, and lichenification are evaluated on a scale of 0 to 3, and value from percentage involvement is on a scale of 0 to 6. Then total EASI score is as follows: $EASI = 0.1 * EASI_{\text{head and neck}} + 0.3 * EASI_{\text{trunk}} + 0.2 * EASI_{\text{upper limbs}} + 0.4 * EASI_{\text{lower limbs}}$	NA: partial assessments cannot be saved.
		
 Change from baseline in EASI score Percent change from baseline EASI score^a 	Change from baseline: observed EASI score – baseline EASI score % change from baseline: $100 \times \frac{\text{Observed score} - \text{Baseline}}{\text{Baseline}}$	Missing if baseline or observed value is missing

		EASI-50 ^a	% improvement in EASI score from baseline $\geq 50\%$: % change from baseline ≤ -50	Missing if baseline or observed value is missing
		EASI-75 ^a	% improvement in EASI score from baseline $\geq 75\%$: % change from baseline ≤ -75	Missing if baseline or observed value is missing
		EASI-90 ^a	% improvement in EASI score from baseline $\geq 90\%$: % change from baseline ≤ -90	Missing if baseline or observed value is missing

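### As-observed IGA and EASI response rates leave out patients whom Protocol 6.3 requires to stop for non-response, so they overstate response in the full treated cohort

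*SAP*

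**What the plan says.** Protocol 6.3 ties leaving the study to treatment failure: "Patients requiring long-term systemic treatment for symptoms of AD (e.g., non-responders) must be discontinued from the study". The same section allows topical agents as needed for flares, and short-term systemic treatment case by case.

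SAP 7.3.1 then defines the as-observed analysis: "For this analysis, only data from completers at the visit are relevant". It applies this to all efficacy and health-outcome endpoints. In Table KGAE.7.3 the rule for IGA (0,1) and EASI-50/75/90 is "Missing if baseline or observed value is missing", so an absent visit value is not counted as non-response.

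As-observed is one of three summaries. SAP 7.10 states: "These summaries will be provided for the data as-observed, and after implementation of LOCF and MCMC-MI imputation methods". SAP 7.11 says the same for the health outcomes. The detailed LOCF and MCMC-MI rules are blacked out in the public SAP.

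SAP 7.14.1 plans subgroup summaries of IGA (0,1) and EASI-75 in the safety population without naming a missing-data method.

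**The concern.** In most studies one has to argue about whether dropout is related to outcome. Here the protocol makes it so for one group: a patient who fails and needs long-term systemic therapy must leave. The as-observed percentage at later visits is then computed without that patient.

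The trial has one arm and no inferential testing, so the response percentages and their confidence intervals are the efficacy result. No control arm would show the same selection and let a reader discount it. SAP 7.10 asks for n explicitly for continuous measures, but only number and percentage for categorical ones, so the shrinking denominator may not be visible. If the as-observed figure is the one taken forward, response at Week 32 or Week 52 will look better than it was among the patients who started.

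**Working it through.** The plan states no response rate, dropout rate or precision target that could be reproduced, and the sample-size basis is redacted. What follows is therefore an illustration over a range.

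**Inputs**
- N = 200, the approximate planned size (Protocol 3.2, SAP 6.1).
- p = response rate in the full treated cohort. Assumed: 40 to 70%.
- d = proportion who have left under Protocol 6.3 by the visit. Assumed: 5 to 20%.
- q = proportion of those leavers who would count as responders at that visit. Assumed: 0, p/2 or p.
- Other missing data are ignored.

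**Formulas**, with R = pN responders and L = dN leavers
- As-observed rate = (R − qL)/(N − L).
- Shift over the full-cohort rate = d(p − q)/(1 − d).

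**p = 50%, all leavers non-responders (q = 0)**
- 5% leaving: 100/190 = 52.6%, shift +2.6 points.
- 10% leaving: 100/180 = 55.6%, shift +5.6.
- 15% leaving: 100/170 = 58.8%, shift +8.8.

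**p = 50%, leavers respond at half the cohort rate (q = 25%)**
- 5% leaving: (100 − 2.5)/190 = 51.3%, shift +1.3.
- 10% leaving: (100 − 5)/180 = 52.8%, shift +2.8.
- 15% leaving: (100 − 7.5)/170 = 54.4%, shift +4.4.

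**Leavers respond at the cohort rate (q = p):** the shift is zero at any d.

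**Shift in points over a range of p, with q = 0**

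| Cohort rate | 5% leave | 10% leave | 15% leave | 20% leave |
|---|---|---|---|---|
| 40% | +2.1 | +4.4 | +7.1 | +10.0 |
| 50% | +2.6 | +5.6 | +8.8 | +12.5 |
| 60% | +3.2 | +6.7 | +10.6 | +15.0 |
| 70% | +3.7 | +7.8 | +12.4 | +17.5 |

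**Counting leavers as failures.** The rate over the full N is (R − qL)/N = p − dq. With p = 50% and d = 10%, this is 50.0% if q = 0, 95/200 = 47.5% if q = 25%, and 90/200 = 45.0% if q = 50%. So when leavers do no better than the cohort, the as-observed rate lies at or above the full-cohort rate, and the failure-counting rate lies at or below it.

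**Change over visits.** Start from 100/200 = 50%. If 20 patients leave and responders among those remaining fall to 90, the as-observed rate is 90/180 = 50%, which is flat.

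**The case against.** The SAP is open about the limitation. It says that "this estimand is conditional and targets the effect of treatment conditional on completion of treatment through the time point of interest", that the result is not causal, and that ICH E9(R1) does not recommend the strategy. It also gives the same endpoints after LOCF and MCMC-MI. Protocol 8.6.2 says: "Patients who discontinue study drug permanently during study participation must be scheduled for an Early Termination visit", and Protocol 7.17 includes IGA, BSA and EASI at that visit. A patient who is failing at early termination would therefore have a failing value to carry forward. Under plain LOCF that patient stays in the full denominator as a failure, with no upward shift by this route. The SAP revision history records that the LOCF and MCMC-MI rules were updated in Version 3 for values collected after treatment discontinuation.

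All of this stands, and it rules out three stronger readings that a reader might infer:

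- *That the plan's efficacy results as a whole are inflated.* The argument reaches only the as-observed summaries.
- *That the plan has no rule counting these exits as failures.* The relevant sections are redacted, so this cannot be said.
- *That response rates must climb from visit to visit.* The flat example shows otherwise. The bias is relative to the full-cohort denominator at the same visit.

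It is also fair that the exit trigger is narrow (long-term systemic treatment), so the number leaving may be small, and that some leavers might have responded later.

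The objection does not remove the need to say which summary is the main one. The readable SAP sets three side by side, and its caveat on completion does not mention that the protocol makes completion depend on response.

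**Conclusion.** The point holds for the as-observed summaries. Whenever patients discontinued under Protocol 6.3 respond less often than the cohort, the as-observed IGA and EASI response rates exceed the full-cohort rate, by d(p − q)/(1 − d). At an assumed 50% rate with all leavers non-responders, that is 2.6 to 8.8 points for 5 to 15% leaving. If the need for long-term systemic treatment is itself regarded as failure, q is zero by definition and the full shift applies. The response rate, the exit rate and the later status of leavers are all assumptions, because the documents give none of them.

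The consequence is moderate. These are secondary, descriptive endpoints, and the primary endpoint (discontinuation of treatment due to adverse events) is unaffected. The correction is a cheap improvement in which figure is presented first and how it is labelled. No finding is made on the redacted imputation rules.

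**What to change.** 1. Leave SAP 7.3.1 as a true as-observed analysis, with no imputation inside it. Label it supportive, for example 'among patients still on treatment', and print the visit n beside the safety-population N.
2. In SAP 7.10 and the 7.14.1 subgroups, name one main summary for IGA (0,1), IGA (0) and EASI-50/75/90. It should keep the safety-population N and count patients discontinued under Protocol 6.3 as non-responders at all later visits. If the redacted LOCF or MCMC-MI rules already do this, name that summary as the main one instead.
3. Identify these patients from the treatment-discontinuation reason and the Atopic Dermatitis Treatments page. The reasons in Protocol 8.6.1 do not include lack of efficacy. The nearest is "requirement for medication or procedure prohibited by the protocol", so the reason alone may not be enough. The treatments page alone may also fall short, because SAP 7.9 uses it for the treatment period and systemic therapy begun after leaving may not appear there.
4. Separately, reconcile Protocol 8.6.2, which lists "Use of rescue medication as outlined in Section 6.3" as a mandatory reason to stop study drug, with Protocol 6.3, which permits topical agents as needed. The two passages determine who leaves, and a literal reading of 8.6.2 would enlarge that group.

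For items 1 to 3 the cost is SAP wording, one derived flag and one extra column. The downside is that reported response rates fall somewhat, and a leaver who would later have responded is counted as a failure. Showing both summaries lets the reader see the distance between them.
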